4.3 Handling of measurements obtained at the premature end of treatment visit

Study participants who withdraw from the study prematurely will be encouraged to return for the PEOT visit. The following rules will apply with regard to the inclusion of the results obtained at the PEOT in the descriptive summaries:

- Any measurements (safety, immunological and PD assessments) conducted at the PEOT should be included in the summaries for the respective scheduled visit, if the PEOT occurs at the time of the next scheduled visit (within the tolerance window specified in the protocol);
- If the PEOT does not correspond to the day of a scheduled visit, the safety and other relevant assessments of the PEOT should be mapped to the nearest scheduled visit, relative to the Baseline visit date, following the last scheduled visit where assessments are available;
- If the date of the PEOT is equidistant between 2 scheduled visits at which no scheduled assessments were performed, the assessments from the PEOT will be mapped to the earliest of these visits.

Different domains from the same PEOT may be re-assigned to different study visits depending on the study schedule of assessments, ie, measurements obtained at the PEOT can only be mapped to a scheduled visit at which the respective assessment was intended to be measured. Assessments from the PEOT that are mapped to scheduled visits will be flagged in the data listings.

Visits after the PEOT following the schedule of the 8-Weeks Observation period, will be mapped to the corresponding planned visit. Assessments on these visits will be flagged in the data listing.

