7.8.3 Rescue medication

If, at any time during this OLE study, a study participant relapses according to the predefined criteria for relapse as specified in Section [4.2.1](#) using the study participant's score on iRODS, INCAT, or maximum grip strength as assessed by the site personnel and supported by the medical judgement of the investigator, then rescue therapy must be considered and the study participant withdrawn from IMP (see Section [6.4](#)). The study participant will return to the SOC Ig treatment (eg, IVIg of 2g/kg) at the investigator's discretion.

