conducted by a healthcare professional visiting the study participant at his/her home; these visits can be conducted at the site as deemed necessary by site personnel and/or study participant.

All study participants who do not continue on rozanolixizumab in an Access Program should perform all visits of the Observation Period, including the FV (scheduled 8 weeks after the final dose of IMP). If at any time during the Observation Period the study participant relapses (according to the medical judgement of the investigator supported by, eg, study participant's score on iRODS, INCAT, or maximum grip strength [assessed by site personnel]), then rescue medication must be considered. The study participant will return to the SOC (ie, Ig treatment) as rescue medication at the time of relapse.

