14.8 Determination of sample size

No formal sample size calculation can be performed. All study participants from the parent study (eg, CIDP01, with a maximum of █ study participants to be randomized) eligible for the OLE will be included.

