After the completion of the Treatment Period(s) (starting at Week 25 for study participants only completing Part 1 or from Week 77 for study participants completing both Part 1 and Part 2 or at any early timepoint in case of PEOT), study participants will enter the 8-week Observation Period where no IMP will be administered. During the Observation Period, study participants will have on-site visits at the entry and exit of the Observation Period (Weeks 25/77, and 32/84, and home visits at Weeks 27/79 and 29/81). Study participants can return to their SOC during the Observation Period. In case the study participant enters an Access Program, no Observation Period will be performed with the exception of the PEOT (Visit 26) Visit which will be immediately completed.

At the discretion of the investigator and/or study participant, home visits can be changed to site visits (eg, for safety reasons). In case an on-site visit cannot be performed, the next visit will be performed at site instead of at home, and all safety assessments that should have been completed at the missed visits will be performed.

The assessments to be completed during each visit are presented in Table 5.1 in the protocol.

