3.9 Changes to protocol-defined analyses

- CIDP relapse (maximum grip strength as assessed by site personnel) is defined as a clinically important deterioration from Baseline in grip strength as measured by site personnel, ie, a decline of $>14\text{kPa}$. Additionally, relapses defined by decline of $>8\text{kPa}$ will be investigated.
- The FAS definition is clarified to include at least one valid post baseline iRODS assessment result.
- The PD-PPS will be handled as a subset of the SS instead of the FAS as defined in the protocol to not exclude data due to missing efficacy results.
- To prevent bias in efficacy evaluation, an efficacy assessment is considered invalid, if that assessment follows the first intake of rescue medication. Assessments on the same day as first intake of rescue medication are considered valid.
- The MFAS is included as an additional analysis set in the SAP and was not part of the final clinical study protocol (CSP). This was added as a sensitivity analysis, to ensure the robustness of the efficacy results in relation to dose variation.
- Elevated liver function tests and potential drug induced liver injury criteria are harmonized across the rozanolixizumab program. Protocol-defined criteria are updated to match UCB's standard evaluations. Please refer to Section 10.3.1 for a list of the criteria that will be evaluated.

$\geq 3\times\text{ULN}$ ALT or AST with coexisting $\geq 2\times\text{ULN}$ total bilirubin in the absence of $\geq 2\times\text{ULN}$ ALP

will instead be defined as

(ALT or AST increase $\geq 3\times\text{ULN}$) and Total bilirubin $\geq 2\times\text{ULN}$ and ALP $<2\times\text{ULN}$ to match program standards and general medical definitions.

- The study variable “Change in CIDP-specific auto-antibody levels in serum from Baseline during Treatment and Observation Periods” will not be analyzed in scope of this SAP.

Sampling dates are captured in the CRF and will be listed. The samples’ results will not be part of this study’s database and instead analyzed and reported separately. The same is true for exploratory biomarkers RNA, proteins and metabolites variables.

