8 EFFICACY ANALYSES

All summaries of efficacy data will be performed on the FAS. Additional outputs are repeated for the MFAS where indicated. Listings will be based on the SS. Treatment group assignment for efficacy data presentation will be according to the actual treatment regimen.

8.1 iRODS

8.1.1 iRODS scores

The iRODS is a linearly weighted patient-reported outcome measure (questionnaire) that specifically captures activity and social participation limitations in patients with CIDP. The iRODS scale was constructed based on the World Health Organization (WHO) International Classification of Functioning, Disability and Health, literature search, and patient interviews.

All 24 items of iRODS meet Rasch model expectations. The questionnaire consists of 24 items (including eating, taking a shower, walking a flight of stairs, standing for hours, etc.) and assesses a patient's perception of their ability to perform daily and social activities. Patients have

3 response options: 0=impossible to perform; 1=performed with difficulty; and 2=easily performed, performed without difficulty.

The raw sum scores of iRODS (range 0 to 48) is an ordinal scale and does not allow for easy interpretation of differences. For this reason, the ordinal scale will be translated to log odds units (logits) scale using the nomogram in [Section 13.1](#), placing patients' estimates on the same logit scale. The primary analysis and iRODS summary will be performed on logit locations. For easier interpretation the person locations (logits) will be translated to centile metric scores changing from 0 (most severe activity and social participation restrictions) to 100 (no activity and social participation limitations).

Both transformed and untransformed data will be listed and summarized by treatment group for each scheduled assessment during the Treatment and Observation Period.

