10.2 Adverse events

Adverse events will be recorded from the time of informed consent until study completion. All AEs will be coded ([Section 3.8](#)) and categorized by relationship to rozanolixizumab.

In addition, AEs will be classified according to the Common Terminology Criteria for Adverse Events (CTCAE) Version 5.0 for severity. For any AEs where it is not possible to provide a CTCAE grading, the events will be assessed using a standard intensity classification (mild, moderate and severe).

A TEAE is defined as any event that was not present prior the first administration of IMP in CIDP04 study or any unresolved event already present before the first administration of IMP in CIDP04 study that worsens in intensity following exposure to treatment until 8 weeks following

the last administration of IMP in CIDP04 study. Adverse events starting before the first administration of IMP in CIDP04 study or later than 8 weeks after the administration of the last IMP will not be considered TEAEs. Such events will be listed only.

Where dates are missing or partially missing, AEs will be assumed to be treatment-emergent unless evidence exists that does not allow the AE to be treatment-emergent. Handling of missing dates/times for classification of AEs as TEAEs is described in [Section 4.2.7](#).

The following rules will be used to assign a TEAE to the study periods:

- **Treatment Period:** a TEAE will be assigned to the Treatment Period for the tabulations if the start date/time of the event is at the time of or after the first administration of IMP in CIDP04 study on Week 1, up to Visit 26/PEOT (non-inclusively).
- **Observation Period:** a TEAE will be assigned to the Observation Period for the tabulations if the start date/time of the event is at or after Visit 26/PEOT till 8 weeks after administration of the last IMP in CIDP04 study.
 - The Observation Period's TEAEs will be stratified by TEAEs of study participants who received/did not receive standard of care treatment (i.e. Ig treatment) between start of the Observation Period and occurrence of the TEAE.

The number and percentage of study participants who experience TEAEs will be summarized by Treatment Period, Observation Period (standard of care treatment status identified by WHODD J06BA01 and J06BA02) and Overall, with respective treatment group. The following summaries will be presented:

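### The SAP has no rule for IgG values drawn after immunoglobulin therapy and invalidates efficacy values only after flagged rescue, so Final Visit summaries (and any PEOT taken after Ig) mix drug withdrawal with Ig treatment

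*SAP*

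**What the plan says.** **Ig after IMP.** SAP 2.3 and Protocol 5.1 allow it without a relapse: "Study participants can return to their SOC during the Observation Period". A participant who relapses on treatment returns to Ig, with IVIg 2 g/kg as the example (Protocol 7.8.3). For a relapse in the Observation Period, Protocol 8.4 says: "The study participant will return to the SOC (ie, Ig treatment) as rescue medication at the time of relapse".

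**IgG and other laboratory data.** SAP 4.3 says of the PEOT visit: "Any measurements (safety, immunological and PD assessments) conducted at the PEOT should be included in the summaries for the respective scheduled visit". A PEOT that does not match a scheduled visit is mapped to the nearest one at which that assessment was planned. SAP 4.2.3 deals only with values that are missing or outside the quantification limits. SAP 9.2.1 summarises total IgG and subclasses by timepoint on the PD-PPS, which removes important protocol deviations (SAP 3.5.6).

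**Efficacy.** SAP 3.9 says that "an efficacy assessment is considered invalid, if that assessment follows the first intake of rescue medication"; 3.5.3 and 4.2.1 repeat this. Rescue is identified by a Yes/No field in the eCRF (SAP 8.5). iRODS data are "summarized by treatment group for each scheduled assessment during the Treatment and Observation Period" (SAP 8.1.1), with similar wording for INCAT, grip strength and RT-MRC.

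**Adverse events.** Here the SAP does separate by Ig. Observation Period TEAEs are "stratified by TEAEs of study participants who received/did not receive standard of care treatment", identified by WHODD codes J06BA01 and J06BA02 (SAP 10.2).

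**The concern.** Infused Ig is itself IgG, so a total IgG or subclass value drawn after an infusion measures donor IgG together with the participant's own recovery from FcRn blockade. For efficacy, Ig is an effective CIDP treatment (Protocol 2). A Final Visit score in a participant back on Ig no longer shows what happens when rozanolixizumab is withdrawn.

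Whether such an efficacy score counts depends on a label. The same product, flagged as rescue, invalidates one participant's score; given as routine standard of care, it leaves another's in the mean. SAP 3.9 gives prevention of bias as the reason for the rescue rule, and that reason applies equally to unflagged Ig.

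At stake are the description of IgG recovery and the only efficacy timepoint after Visit 26. The study is single-arm and descriptive ("No formal sample size calculation can be performed", Protocol 14.8), so the by-visit summaries are the result, and no model adjusts them afterwards.

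**Working it through.** The plan gives no figure on this point to reproduce. The check has two parts.

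**1. Which values a rule catches**

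| Value | Ig flagged as rescue | Ig as routine standard of care |
|---|---|---|
| Total IgG, subclasses at Final Visit (Week 32/84) | no rule | no rule |
| Total IgG, subclasses at PEOT, mapped | no rule | no rule |
| Tetanus/influenza titres at Visit 26/PEOT | no rule | no rule |
| iRODS, INCAT, grip strength at Final Visit | invalid | kept |
| RT-MRC at Final Visit, Week 32 | invalid | kept |
| Efficacy at PEOT, mapped | invalid | kept |

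The schedule sets the limits of this table:
- Titres are last drawn at Visit 26 and are not on the Final Visit list (Protocol Table 5-1, 8.4.1, 8.4.3).
- Footnote x of Table 5-1 removes RT-MRC at the Final Visit after Part 2, so Week 32 is the only such timepoint.
- Contamination at PEOT requires Ig before that visit, which is to be held as close as possible to the withdrawal decision (Protocol 8.5).
- The Final Visit is 8 weeks after the last dose. The example IVIg interval in inclusion criterion 6 is 2 to 6 weeks, so a participant who resumes promptly would usually have been infused before it.

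**2. Illustrative size for IgG**

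Inputs from the documents:
- 2 g/kg, the relapse example (Protocol 7.8.3).
- 0.4 g/kg, from the monthly minimum for participants entering after a gap (exclusion criterion 18), used here as a low maintenance dose.
- IgG half-life of 3 weeks (Protocol 2).

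Assumed, not in the documents: an IgG distribution volume of 0.05 to 0.10 L/kg, and a share f of participants given Ig.

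Formulas:
- initial rise = dose / volume
- residual = rise × 0.5^(days/21), with 0.5^(7/21) = 0.794 and 0.5^(49/21) = 0.198
- shift in the visit mean = f × residual

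For example, 0.4/0.10 = 4 g/L and 0.4/0.05 = 8 g/L; 2/0.10 = 20 g/L and 2/0.05 = 40 g/L.

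| Single dose | Initial rise (g/L) | After 7 days | After 49 days |
|---|---|---|---|
| 0.4 g/kg | 4 to 8 | 3.2 to 6.4 | 0.8 to 1.6 |
| 2 g/kg | 20 to 40 | 15.9 to 31.7 | 4.0 to 7.9 |

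Shift in the mean at a Final Visit 49 days after a single dose:

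| Share given Ig | 0.4 g/kg (g/L) | 2 g/kg (g/L) |
|---|---|---|
| 10% | 0.08 to 0.16 | 0.40 to 0.79 |
| 25% | 0.20 to 0.40 | 0.99 to 1.98 |
| 50% | 0.40 to 0.79 | 1.98 to 3.97 |

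If the sample comes 7 days after Ig and f = 25%, the shift is 0.8 to 1.6 g/L (0.4 g/kg) or 4.0 to 7.9 g/L (2 g/kg). For scale, the protocol acts on IgG at 1 and 2 g/L (6.4.1.2, 6.4.1.3).

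Two influences pull in opposite directions. Repeat infusions leave more than a single dose. While FcRn is still blocked, IgG clears faster than the 3-week half-life implies (Protocol 2), so less remains.

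**The case against.** The strongest reply is that the consequence is limited. The primary objective is safety and the IgG analyses are exploratory. Time to relapse is confined to the Treatment Periods. Medications are listed with dates, and mapped PEOT values are flagged in the listings. Keeping Final Visit data whatever permitted treatment followed is a legitimate choice if labelled. All of this stands as a limit on importance. But the SAP does not label the choice, and its own rescue rule goes the other way.

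A reader might infer more than the documents support:
- *That on-treatment IgG means are generally inflated by mapped PEOT values.* This needs Ig before a visit meant to follow the withdrawal decision closely.
- *That the PD-PPS cannot catch any of it.* The deviation specification is a separate document and cannot be checked here. Ig is prohibited during the Treatment Period (Protocol 7.8.2), SAP 6.4.2 assigns medication taken before Visit 26/PEOT to that period, and SAP 3.5.6 permits exclusion of specific data. Some pre-PEOT Ig might therefore be removed, although nothing requires it. SAP 3.2.1.2 points the other way, since it starts the Observation Period straight after the last dose.
- *That titres at the Final Visit, or RT-MRC at Week 84, are affected.* Neither is scheduled.
- *That a rise of 20 g/L or more is typical.* That follows the relapse example. The efficacy gap concerns non-relapse Ig, for which the only dose figure is the 0.4 g/kg/month entry minimum.
- *That minimum IgG and maximum decrease are distorted.* Donor IgG raises the level, so these are little affected.

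**Conclusion.** The gap is real. It is clearest at the Final Visit, where total IgG and subclasses have no Ig rule at all, and where iRODS, INCAT and grip strength (RT-MRC at Week 32) are protected only if the Ig was flagged as rescue. It extends to PEOT values taken after Ig, and at Visit 26/PEOT to tetanus and influenza titres, but that part is narrower and may be partly caught by a deviation specification that is not in the documents.

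Under the assumed volume and the protocol's half-life, one infusion leaves between 0.8 and 7.9 g/L of donor IgG seven weeks later, depending on dose and volume. The effect on a visit mean scales with the share of participants back on Ig, which is not given and could be small or large. The effect on efficacy scores cannot be sized from the documents. SAP 10.2 shows that the sponsor can already identify the event, so the SAP should be amended before database lock.

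**What to change.** Leave the existing rescue rule as it is and add three items.

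- **SAP 8 and 9.2.1:** present Observation Period (Final Visit) total IgG, IgG subclasses and efficacy split by whether Ig was received between the last IMP and the assessment, using J06BA01/J06BA02 as in SAP 10.2.
- **SAP 4.2.3, 4.2.4 and 4.3:** do not map PEOT values of total IgG, IgG subclasses or tetanus/influenza titres drawn after any post-IMP Ig, flagged as rescue or not, to Treatment Period visits. List and flag them. State that they do not count as missing under the 33% rule; otherwise the exclusion could suppress a whole summary.
- **SAP 3.5.3, 3.9 and 4.2.1:** add that PEOT efficacy values taken after any post-IMP Ig are likewise not mapped to Treatment Period visits.

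State the convention for Ig given on the day of the sample, because SAP 4.2.7 notes that medication times are not recorded.

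The cost is SAP text and one derived flag from concomitant medication data already collected. Clinical management does not change. The downside is smaller cells at the Final Visit. The Ig yes and no groups are self-selected, so the split is descriptive and should not be read as a comparison of treatments.

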4.4 Data monitoring committee (DMC)

A DMC will systematically monitor and report on the progress, safety, and/or critical efficacy endpoints of this study by convening to review the ongoing safety and efficacy data. The DMC

will also review the impact of infusion rate on local and systemic tolerability during the first 2 doses.

4.4.1 Timing of DMC

DMC meetings for CIDP04 will take place in conjunction with CIDP01 DMC meetings. Once CIDP01 is completed, additional meetings for CIDP04 may be organized as agreed with the DMC members.

4.4.2 Data required for DMC

The analyses and data required for DMC review are described in a separate DMC SAP and include all data specified in the DMC Charter.

4.5 Multicenter studies

Individual center results will not be displayed.

4.6 Multiple comparisons/multiplicity

Not applicable.

4.7 Use of an efficacy subset of study participants

Not applicable.

4.8 Active-control studies intended to show equivalence

Not applicable.

4.9 Examination of subgroups

Not applicable.

5 STUDY POPULATION CHARACTERISTICS

5.1 Study participant disposition

The number of participants who were enrolled, dosed, participants included in each analysis set, and participants who completed or prematurely discontinued the study, as well as the reason for discontinuation, and discontinuation due to AEs (categorised as fatal, non-fatal, other) will be presented by treatment group and overall. Screen failure reasons will be summarized, based on the ES.

In addition, the following listings will be presented by treatment group:

- Participant disposition (ES)
- Study discontinuation (ES)
- Visit dates (SS)
- Participant analysis sets (ES)

Study participant disposition will be listed based on the ES by treatment group, and will include the date of informed consent, date and time of first and last dose of IMP, date of premature termination and primary reason, and date of final contact (if applicable).

The first dose of IMP will be the first IMP infusion in CIDP01 for study participants treated with rozanolixizumab in CIDP01 or the first dose of rozanolixizumab in CIDP04 for the study participants under placebo in CIDP01.

The listing of study discontinuation will include the reason for discontinuation, period of discontinuation, with dose and number of days on that dose and the total number of days on study medication.

The number of days on IMP will be calculated as follows:

Number of days on IMP=(Date of Last Dose Received)-(Date of First Dose Received)+1

Time to discontinuation of study participation will be listed and plotted in a Kaplan-Meier-Curve for all discontinuations versus discontinuation due to COVID-19. The plot will be based on the randomized set.

Reasons for screening failures, disposition and discontinuation reasons will also be summarized based on the respective event's date relative to the COVID-19 period.

5.2 Protocol deviations

Important protocol deviations (IPDs) will be identified and classified by the deviation types identified in the IPD document. A listing of all IPDs identified at the Data evaluation meetings (DEM) will be presented for all participants in the SS, and will include the deviation type and description. The number and percentage of participants in the SS with IPDs will be summarized overall if appropriate. The denominator for percentages will be the number of participants in the SS.

A separate listing will present the captured data from the "COVID-19 Impact" eCRF form. Frequencies of impact categories by visit will also be presented for each COVID-19 relatedness category (suspected, confirmed, general or other reasons).

Important protocol deviations will be summarized by COVID-19 period and relationship to COVID-19 (any, related, not related). Number and percentage of participants with these protocol deviations will be summarized for the SS.

Important protocol deviations will also be presented by COVID-19 period (pre- or during). A post- COVID-19 period may be added if applicable.

Start of the pandemic will be the date the WHO recognized COVID-19 as pandemic, 20 March 2020. The cut-off date for the post- subgroup level will be defined prior to database lock if applicable, an update to the pre-COVID-19 cut-off date may be performed. Details of the analyses will be specified in the following sections.

A date is considered pre COVID-19 up to the day before the start date, so 19 March 2020.

